## 3. Study subjects

Actual subject recruitment will start after ethics committee (EC), competent authority (CA) and clinic approvals have been granted. The study subjects will be recruited and screened in a single center (Aurora hospital, Infectious diseases clinic, HUH, Helsinki). All the eligible study subject candidates will be contacted during regular visits and informed of the study by study investigators verbally and with a written information hand out. After adequate time and opportunity to inquire about details of the study and to decide whether or not to participate in the study, the candidates will sign and personally date an informed consent. After the study has finished, all the study subjects will continue their regular follow up with a chance to continue their current ART or to switch to another regimen.

The total number of study subjects included in the study is 45. Study subjects will be randomized 1:1 to continue current ART regimens or to switch their PI or efavirenz to once daily raltegravir

plus continue current NRTIs. The randomization will be stratified by age, sex and antiretroviral regimens (PI or efavirenz).

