## 6. Data analysis

The data will be analyzed by the investigators and the study group.

All variables of the data will be analyzed after the last subject's last visit, when the data have been declared complete.

The data will be analyzed using IBM SPSS Statistics v. 22. The differences between the groups will be analyzed by using chi-square, Fisher's exact, Mann-Whitney U test and others, as appropriate.

As there are no earlier ART-switch studies using H-Magnetic resonance spectroscopy for the quantification of liver fat, the calculation of the study power is an estimate. In the STERAL study evaluating the effect of switching from efavirenz (EFV) to RAL vs. continuing Efv-based ART, a statistically significant difference in the liver fat content using CAP (controlled attenuated parameter) was shown with a study sample of 19 +18 subjects after 48 weeks (7,3% decrease in the RAL vs. 11,0% increase in the Efv arm, p = 0,019) (11).

The power of this study is calculated with the assumption of liver fat being 4.4-5.0% in this study group at baseline. This estimation is based on our previous results published in 2002, when the median liver fat was 8% with lipodystrophic patients and 3% with non-lipodystrophic patients (17). Hadigan et al reported liver fat content being >5% in 42% of HIV positive subjects (18). As the liver fat content correlates with visceral fat mass, studying overweight or obese patients with at least one metabolic syndrome component includes patients at high risk for elevated liver fat content.

In the power calculation, we have used a coefficient of variation (CV) of H-Magnetic resonance spectroscopy being 11% (17). To detect a 9% difference between study arms with 80% power, a minimum sample size of 25 + 25 subjects with a 10% drop-out rate is needed.

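### Section 3 enrols 45 subjects, below the 25 + 25 that section 6 calls the minimum for 80% power; at 45 with 10% loss, two-sided power is about 68–78%

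*Combined protocol and SAP*

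**What the plan says.** Section 6 (Data analysis) of the combined protocol and SAP holds the only sample-size justification. It assumes "the assumption of liver fat being 4.4-5.0% in this study group at baseline", takes the CV of the spectroscopy method as 11%, and sets 80% power for a 9% difference as the target. Its conclusion is that "a minimum sample size of 25 + 25 subjects with a 10% drop-out rate is needed". It also concedes that "the calculation of the study power is an estimate", because no earlier switch study had used spectroscopy.

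Section 3 (Study subjects) gives a different total: "The total number of study subjects included in the study is 45". The next sentence begins "Study subjects will be randomized 1:1 to continue current ART regimens".

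Neither section states alpha, sidedness, the test behind the calculation, the scale of the 9% difference, or the evaluable number per arm before drop-out. Section 6 lists Mann-Whitney U among several possible tests and fixes none for the primary endpoint.

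**The concern.** Section 6 describes 25 + 25 as a minimum that goes with a 10% drop-out rate. Section 3 enrols five fewer. The plan therefore recruits below its own stated requirement and keeps the 80% claim.

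A second difficulty is that the calculation cannot be traced. A reader cannot tell whether 25 per arm is the number to randomise or the number to analyse, so the size of the shortfall is not visible either.

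The calculation supports the single primary objective, the 24-week change in liver fat. If the power is overstated, a null result will be taken as stronger evidence of no difference than it is.

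**Working it through.** **Inputs.** Difference 9%, CV 11%, power 80%, drop-out 10% (section 6); allocation 1:1 and 45 subjects (section 3). Assumed, because not stated: alpha 0.05, two-sided. The 11% is taken at face value as the relevant variability.

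**Formulas.**
- Normal approximation: n per arm = 2(1.960 + 0.842)²/d²; power = Φ(d√(n/2) − 1.960).
- t-test: noncentral t with 2n − 2 degrees of freedom and noncentrality d√(n/2).
- Drop-out: n/0.9.

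**Standardised difference d under three readings.**
- A. 9 against an SD of 11: d = 9/11 = 0.818.
- B. Relative reduction, ratio 0.91. Log scale: ln(1/0.91)/√ln(1 + 0.11²) = 0.0943/0.1097 = 0.860. CV applied to each arm's mean: 0.09/√[(0.11² + 0.1001²)/2] = 0.856.
- C. Relative increase, ratio 1.09. Log scale: 0.0862/0.1097 = 0.786 (0.783 with a log SD of 0.11). CV applied to each arm's mean: 0.782.

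**Reproducing 25 + 25.**
- A: normal 2 × 7.849/0.669 = 23.45, so 24; t-test 24.45, so 25. Here 25 is the evaluable number, and drop-out would raise it to 25/0.9 = 27.8, so 28 (normal: 24/0.9 = 26.7, so 27).
- B: normal 22, and 22/0.9 = 24.4, so 25. The t-test gives 22.2–22.4 before rounding, and dividing by 0.9 gives 24.7–24.9, so 25 (rounding up to 23 first gives 26). Here 25 already includes drop-out.
- C: normal 26, then 29; t-test 27, then 30. This does not reproduce 25.

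The stated figure can therefore be reached in two ways, one without and one with a drop-out allowance.

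**Power after 10% loss.** 50 enrolled leaves 50 × 0.9/2 = 22.5 per arm; 45 enrolled leaves 45 × 0.9/2 = 20.25 per arm.

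| Reading | 50 enrolled, t-test / normal | 45 enrolled, t-test / normal |
|---|---|---|
| A. SD 11 | 76.5% / 78.4% | 71.8% / 74.0% |
| B. Ratio 0.91 | 80.1–80.5% / about 82% | about 76% / about 78% |
| C. Ratio 1.09 | about 73% / about 75% | about 68% / 70–71% |

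Example (A, normal, 45 enrolled): 0.818 × √10.125 = 2.603; 2.603 − 1.960 = 0.643; Φ(0.643) = 0.740.

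**Detectable difference (A, t-test, 80% power).** 9.4% with 50 enrolled and 9.9% with 45 enrolled, both after 10% loss.

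**Test.** If Mann-Whitney U were used, with an assumed efficiency of 0.955, the t-test powers would fall by about a further 2 points.

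**The case against.** Four objections deserve an answer.

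1. **25 + 25 may already contain the drop-out allowance.** This stands. A CV paired with a percentage difference can naturally be read on a relative scale, and reading B then gives 25 per arm after drop-out and at least 80% power at 50. A reader might infer that no inflation was applied, that power misses 80% whichever enrolment figure is used, and that the right target is 28 per arm. The documents do not support that: it treats the CV as an additive SD, which the plan never says. Even on reading A the shortfall at 50 is modest (1.6 points by normal approximation), and section 6 calls the calculation an estimate.

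2. **45 may be the completers.** The arithmetic fits, since 50 × 0.9 = 45, and 45 completers (22.5 per arm) would have the power shown for 50 enrolled. But section 3 speaks of subjects included and goes straight on to their randomisation. That describes enrolment.

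3. **The test may be one-sided.** On reading A, one-sided 5% power at 45 with loss would be 81.9–83.1%. But no one-sided test is stated, and that calculation gives 22 (normal) or 23 (t-test) per arm after drop-out, not 25.

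4. **This is ambiguity, not error.** That is fair for 50. It is not fair for 45, where every two-sided reading tried falls short and where the plan goes below a number it calls a minimum.

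**Conclusion.** The concern holds for the enrolment in section 3. With 45 randomised and 10% lost, power to detect the planned difference is about 68–78% rather than 80%. On the simplest reading (A) it is about 72% by t-test, with a detectable difference of about 9.9% rather than 9%.

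For 50 enrolled, the plan cannot be called right or wrong without knowing the scale it used.

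The conclusion rests on a two-sided 5% test, on 45 being the number randomised, and on 11% being the relevant variability. Section 6 describes that 11% as the CV of the measurement method; whether it represents the spread of 24-week changes between subjects is a separate question, not settled here.

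**What to change.** - Use one enrolment number in sections 3 and 6, and say whether it is the number randomised or the number evaluable.
- In section 6, state the alpha, sidedness, scale of the 9% difference, test and evaluable number per arm actually used, and show the division by 0.9. The sponsor should recover these from the calculation that was run; 28 per arm should not be written in on the strength of one reading.
- If enrolment stays at 45, replace the 80% with the power for that number (about 72% by t-test on the SD-11 reading), or give the difference detectable with 80% power (about 9.9%). If another scale was used, give the matching figure for that scale.

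This takes a few sentences in two sections and no extra subjects. The cost is a stated power that looks less favourable.

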### Publication plan

We anticipate to submit one main manuscript with the results of the primary objective (liver fat change) and secondary objectives (1-3: body composition change as well as metabolic markers). Additional manuscripts will be submitted after further analysis of subcutaneous fat samples (for transcriptional, protein and other biochemical analyses), fecal samples (microbiota) and blood samples (inflammatory markers and metabolomics studies).

## 7. Study budget

Study budget is detailed in a separate sheet "Study Budget" attached.

## 9. List of attachments:

1. Synopsis
2. CVs of Principal Investigator and Head of the Obesity Research Unit
3. SmPC of Isentress
4. Study budget
5. Patient registry report
6. Summary of the current state of the report to the national competent authority (Fimea)
